#### 4.5.9 LID MARGIN ASSESSMENT

---

The participant will be seated at a slit lamp biomicroscope.

##### **Vascularity of the margin (erythema)**

The vascularity of the lid margin will be graded (0-4 scale; 0: none, 1: minimal, 2: mild, 3: moderate, 4: severe).

##### **Amount of lash loss**

The amount of lash loss will be assessed (0-4 scale; 0: none, 1: minimal, 2: mild, 3: moderate, 4: severe).

##### **Lid margin edema**

The presence or absence of lid margin edema will be recorded.

##### **Lid margin telangiectasia**

Lid margin telangiectasia will be graded (0-4 scale, 0: none; 1: single telangiectasia; 2: 2 to 5 telangiectasia; 3: >5 telangiectasia; 4: severe - entire lid involvement).

##### **Tear film debris**

The presence or absence of tear film debris will be recorded.

#### 4.5.10 SLIT LAMP BIOMICROSCOPY

---

A slit lamp biomicroscopy examination will be conducted to assess anterior segment ocular health. Ocular findings will be graded using the Efron grading scale (0-4, 0.5 steps – unless otherwise stated):

##### **External adnexa anomalies**

The presence or absence of external adnexa anomalies will be recorded. If adnexa anomalies are detected, the anomaly will be described.

##### **Bulbar and limbal hyperemia**

The redness of the bulbar and limbal conjunctiva of both eyes will be assessed using the Efron Grading scale (0 to 4, 0.5 steps).

##### **Scars or other corneal observations**

The presence or absence of scars or other corneal observations will be recorded. If scars or other corneal observations are detected, the finding(s) will be described.

##### **Infiltrates**

The presence or absence of infiltrates will be recorded. If present, the number and location will be recorded. The size (diameter in mm) and depth of the largest infiltrate (0-4 scale, 1 step) in the central, mid-periphery and periphery will be noted.

##### **Endothelium abnormalities:**

The presence or absence of endothelium abnormalities will be recorded. If endothelium abnormalities are detected, the finding(s) will be described.

##### **Anterior chamber**

The presence or absence of anterior chamber reaction will be recorded. If an anterior chamber reaction is detected, the finding(s) will be described.

##### **Other abnormalities**

The presence or absence of other abnormalities will be recorded. If other abnormalities are detected, the finding(s) will be described.

##### **Corneal and conjunctival staining**

A sodium fluorescein strip, wetted with a few drops of saline, will be applied to the superior bulbar conjunctiva of both eyes. Corneal staining type will be graded using the Efron scale (0 to 4, 0.5

steps), staining extent and depth will be graded on a 0 to 4 scale (1 step increment) while viewing with cobalt blue light and Wratten filter (if available). Conjunctival staining will be graded using a 0 to 4 scale (0.5 steps), with larger values indicating increasing severity.

#### **Palpebral conjunctival hyperemia and papillae (roughness)**

The redness and roughness of the upper and lower eyelids will be assessed using the Efron scale (0 to 4, 0.5 steps).

#### 4.5.11 MEIBOGRAPHY

---

While seated at the OCULUS Keratograph® 5M, the participant will be asked to place their chin on the chin rest and head against the forehead rest. The lower lid will be everted with the investigator's thumb to expose as much of the palpebral conjunctiva as possible. At least one clear infrared image will be taken of the exposed palpebral surface. The upper lid will be everted with a cotton tipped applicator and at least one clear image will be taken. The amount of missing glandular tissue in each lid will be graded from the images using the following Arita et al. scale: Grade 0 = no MG loss, Grade 1 = area of loss less than 1/3 of the total MG area, Grade 2 = area of loss between 1/3 and 2/3 of the total MG area and Grade 3 = area of loss greater than 2/3 of the total MG area. The grade of the lower lid and upper lid will be summed for each eye (Total Meiboscore).

#### 4.5.12 ANTERIOR EYE PHOTOGRAPHS

---

The participant will be seated at a Zeiss slit lamp attached to a Canon EOS 60D digital camera. A photograph of each eye will be taken at 5x magnification with additional external illumination provided by a Canon Macro Twin Lite flash. The participant will hold a ruler underneath each eye while the photographs are taken. The ruler will serve as a calibration reference when the images are analysed with ImageJ in order to determine the size of the ocular surface in mm^2. The ruler will be cleaned with an alcohol wipe prior to being given to each participant.

#### 4.5.13 MEASUREMENT OF VOLUME INSIDE THE GOGGLE

---

The participant will be seated in a consulting chair and will be asked to rest their head on the headrest. A pair of swimming goggles (Arena Zoom X-Fit), which are the same make and model as the prototype evaporimeter, will be used. The swimming goggle has been modified by drilling a small hole into the top of each lens. The participant will be asked to place the goggle over both eyes and to tighten the strap. A plastic, needleless syringe, with a 200 µl pipette tip attached to the end of the syringe, will be filled with saline (Bausch & Lomb Sensitive Eyes Saline Plus).

Participants will be asked to keep their eyes closed while saline is added to the goggle. Saline will be added to each swimming goggle until the goggle has been filled with saline. The amount of saline added to each goggle will be recorded in milliliters. When the goggle is ready to be removed, the participant will be advised to tilt their head forward and continue to keep their eyes closed. A plastic tub will be placed below the participant's face and paper towels will be placed around the goggle to catch any saline that may spill out of the goggle. When the goggle has been removed, the participant will be advised to wipe their face with a paper towel while their eyes are kept closed. The swimming goggle will be cleaned with an alcohol wipe prior to use on each participant. A new syringe will be used for each participant. New saline and a new pipette tip be used to fill each goggle.

#### 4.5.14 SLIT LAMP BIOMICROSCOPY (SAFETY VARIABLE)

---

The participant will be seated at a slit lamp at the following will be assessed in both eyes for:

##### **External adnexa anomalies**

The presence or absence of external adnexa anomalies will be recorded. If adnexa anomalies are detected, the anomaly will be described.

##### **Bulbar and limbal hyperemia**

The redness of the bulbar and limbal conjunctiva of both eyes will be assessed using the Efron Grading scale (0 to 4, 0.5 steps).

##### **Scars or other corneal observations**

The presence or absence of scars or other corneal observations will be recorded. If scars or other corneal observations are detected, the finding(s) will be described.

##### **Infiltrates**

The presence or absence of infiltrates will be recorded. If present, the number and location will be recorded. The size (diameter in mm) and depth of the largest infiltrate (0-4 scale, 1 step) in the central, mid-periphery and periphery will be noted.

##### **Corneal and conjunctival staining**

A sodium fluorescein strip, wetted with a few drops of saline, will be applied to the superior bulbar conjunctiva of both eyes. Corneal staining type will be graded using the Efron scale (0 to 4, 0.5 steps), staining extent and depth will be graded on a (0 to 4 scale, 1 step) while viewing with cobalt

blue light and Wratten filter (if available). Conjunctival staining will be graded using a 0 to 4 scale (0.5 steps), with larger values indicating increasing severity.

#### 4.5.15 APPLICATION OF PETROLEUM JELLY

---

Petroleum jelly will be removed from the original container using a cotton tipped applicator and placed in a new paper cup for each participant. Another cotton tipped applicator will be given to each participant to apply thin layer of petroleum jelly to the skin surrounding the eye using a mirror. A new cotton tipped applicator and paper cup will be used for each application. Any remaining petroleum jelly will be disposed of according to UW guidelines.

#### 4.5.16 REMOVAL OF PETROLEUM JELLY

---

To remove petroleum jelly from the skin, the participant will close their eyes and wipe with a tissue in a nasal to temporal direction, with extra care being paid when wiping near the lid margin to avoid contaminating the tear film.

#### 4.5.17 SUBJECTIVE COMFORT RATINGS

---

Participants will be asked to fill a numerical analog scale for comfort, dryness, and burning or stinging for each eye on a 0-100 scale at the following time points during Visit 2:

- Before eye drop instillation (prior to the first baseline evaporimetry measurement)
- Before eye drop instillation (at least 20 minutes after the initial baseline evaporimetry measurement)
- 10 minutes after eye drop instillation
- 30 minutes after eye drop instillation
- 60 minutes after eye drop instillation

#### 4.5.18 EVAPORIMETRY

---

The participant will be seated at an adjustable height table and will place their elbows on the table. The participant will hold a pair of modified swimming goggles (Figures 1A and 1B) over their eyes for 20 seconds while their eyes are open. The participant will be prompted to blink every 3 seconds during the measurement using a metronome (<https://www.youtube.com/watch?v=9ypeNJJeKIs>). The goggle will be removed and ventilated in front of a fan until the relative humidity returns to baseline levels. The goggle will then be placed over the eyes for 20 seconds while they are closed to measure the evaporation rate from the skin. Three consecutive measurements of open eye and closed eye measurements will be taken. Recordings of the temperature and relative humidity during the measurement will be saved as a word document and images of the temperature and

humidity versus time plotted as a graph will be saved as a png file. The rate of tear evaporation will be calculated from slope derived from the change in relative humidity over time. The evaporation rate from the ocular surface will be calculated by subtracting the evaporation rate of closed eye from the evaporation rate of the open eye. The average of three ocular surface evaporation rates will be calculated for each eye.

[figure not shown]

Figure 1: (A) Evaporimeter with arrows showing the location of the temperature/humidity sensors in the swimming goggles. (B) View of the front of the evaporimeter.

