## 1 INTRODUCTION

The worldwide prevalence of dry eye is estimated to be approximately 5% to 50%. Dry eye is classified into three main subtypes: aqueous deficient, evaporative, and mixed. In order to effectively treat patients, it is important for eye care practitioners to be able to differentiate between the different causes of dry eye.

One non-invasive method of assessing the rate of evaporation of the tear film from the front surface of the eye is by using a technique called evaporimetry. At present, there is only one commercial evaporimeter, the Eye-VapoMeter (Delfin Technologies Ltd., Finland), available for clinical use. The Eye-VapoMeter was initially designed as a dermatological device to measure the rate of skin evaporation. The device was modified by incorporating an eye cup from a swimming goggle onto the base of the instrument and was validated for ocular use in 2014.

All other evaporimeters previously described in the literature have only been used within a research setting. To our knowledge, there has only been one previous evaporimeter, developed by Tsubota and Yamada in 1992, which was capable of binocularly measuring the tear evaporation rate (TER).

The 2017 TFOS DEWS II Tear Film report noted that there is currently a lack of reliable, commercially available evaporimeters and stressed that the development of evaporimeters that can be used in a clinical setting under a variety of temperatures and humidities would be extremely useful. To overcome various problems associated with the Eye-VapoMeter and the Yamada/Tsubota evaporimeter, a novel, prototype goggle-based evaporimeter has been designed to simultaneously measure TER from both eyes at the same time. The benefit of a simultaneous TER measurement is less chair time for both the patient and practitioner.

Due to the relative lack of previously published research investigating evaporimetry and eye drops, the purpose of this pilot study is to compare the effect of an eye drop (Systane® Complete) on TER. Systane® Complete was released in Canada in 2018 for the treatment of both aqueous deficient and evaporative dry eye. The study will also serve to validate the use of the novel, in-house developed evaporimeter for use in non-contact lens wearing participants.

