### 3 HYPOTHESIS

The study hypothesis is that instillation of an eye drop will result in lower tear evaporation rates compared to before the eye drop has been inserted.

The second study hypothesis is that dry eye participants will have higher baseline rates of tear evaporation compared to non-dry eye participants.

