#### 4.1.2 RANDOMIZATION

---

There will be no randomization in this study.

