#### 4.2.2 NUMBER OF PARTICIPANTS

---

Up to 60 participants will be recruited / screened using CORE records and advertising approved by the UW Office of Research Ethics, with a target of 10 dry eye and 10 non-dry eye participants completing the study. At least 20 participants will have the study product instilled at Visit 2. Informed consent will be obtained for all participants prior to their enrolment in the study.

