#### 4.4.1 STUDY VISITS

---

This study has a total of 2 study visits, including the screening visit. Visit 2 will be scheduled up to 14 days after the screening visit (Visit 1). The total time commitment for the scheduled visits is 4 hours of active participation. The summary of visit codes is shown in Table 2.

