**Table 2: Summary of visit codes**

Visit #	Visit code	Study Day	Visits	Duration (hours)
1	V1 (V1-R1 for rescreening)	1	Screening	1.5
2	2	2	Data collection & study exit	2.5

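### The Hypothesis 2 comparison of dry eye and non-dry eye groups is unprotected against a chance or calendar imbalance in room humidity, although the starting humidity and temperature are already recorded

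*Combined protocol and SAP*

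**What the plan says.** Section 3 states as the second hypothesis that "dry eye participants will have higher baseline rates of tear evaporation compared to non-dry eye participants". Group is fixed at screening by OSDI and NIKBUT (Section 4.2.3), and Section 4.1.2 confirms: "There will be no randomization in this study". Recruitment runs "with a target of 10 dry eye and 10 non-dry eye participants completing the study" (Section 4.2.2). Each participant's Visit 2 may fall up to 14 days after screening (Section 4.4.1), and no rule links the dates of the two groups.

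The primary outcome is the slope of in-goggle relative humidity over a 20-second hold. On resetting the goggle, Section 4.5.18 says only: "The goggle will be removed and ventilated in front of a fan until the relative humidity returns to baseline levels". The closed-eye rate is then subtracted from the open-eye rate to remove skin evaporation. Temperature and humidity during each measurement are saved.

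The one environmental provision is the adaptation period of at least 15 minutes in Section 4.4.3. No humidity or temperature range is set for the room. Table 4 uses the recordings only to obtain the slope. It lists a repeated-measures analysis and a paired t-test for the drop, plus correlations. It contains no dry eye versus non-dry eye test and no humidity or temperature covariate.

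**The concern.** Water leaves the eye at a rate driven by the vapour-pressure gap between the ocular surface and the air in the goggle. A fan moves room air, so the level to which the goggle returns is, by inference, the room's level that day. The same eye would then give a higher rate on a drier day. Adaptation fits the participant to that day's room; it does not make one day's room like another's.

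The subtraction does not remove this. If the open-eye rate is a skin term plus k × gap, and the closed-eye rate is the skin term alone, the difference is k × gap. The skin term cancels, but the ambient gap still multiplies what is left.

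At stake is the reading of Hypothesis 2. If one group happens to be seen in drier air, the result alone cannot tell humidity from disease. That matters for a study meant to help validate the device (Section 1) and to inform later sample sizes (Section 4.2.1).

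**Working it through.** The documents give no effect size, SD, power or humidity figure, so there is no stated number to reproduce. The temperatures, humidities and between-person coefficients of variation (CV) below are assumptions.

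**Are several days unavoidable?** Table 2 gives 2.5 h for Visit 2, so 20 completers × 2.5 h = 50 h of sessions. With participants seen one at a time, that takes several days. It does not imply several seasons.

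**Size of the bias.** Let es(T) be saturation vapour pressure by the Magnus formula: es(34 C) = 53.09 hPa and es(22 C) = 26.37 hPa. Then gap = es(eye) − RH × es(room).

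| Room RH | Gap (hPa) |
|---|---|
| 20% | 47.82 |
| 30% | 45.18 |
| 35% | 43.86 |
| 45% | 41.23 |
| 50% | 39.91 |

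- 35% to 45%: 41.23 / 43.86 − 1 = −6.0%
- 30% to 50%: 39.91 / 45.18 − 1 = −11.7%
- 20% to 50%: 39.91 / 47.82 − 1 = −16.5%

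With the eye at 33–35 C and the room at 21–23 C, the 20% to 50% change ranges from −14.5% to −18.9%, and the 35% to 45% change from −5.2% to −6.9%. The gap is linear in RH, so the bias shrinks in proportion as the groups' mean humidities come closer.

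**Effect on a 10 versus 10 comparison.** I simulated a two-sided t-test at 0.05 with lognormal rates and a within-group RH SD of 5 points. The plan does not state sidedness.

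| Dry eye RH vs non-dry eye RH | True ratio | Declared 'dry eye higher', CV 30% | CV 50% |
|---|---|---|---|
| 40 vs 40 | 1.0 | about 2.5% | about 2.5% |
| 35 vs 45 | 1.0 | about 6% | about 4% |
| 20 vs 50 | 1.0 | about 25% | about 12% |
| 40 vs 40 | 1.4 | about 65% | about 29% |
| 45 vs 35 | 1.4 | about 48% | about 21% |
| 50 vs 20 | 1.4 | about 19% | about 9% |

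**Noise if the groups are balanced.** For RH spread uniformly over 20–50%, its SD is 0.30/√12 = 0.0866. The gap CV is 0.0866 × 26.37 / 43.86 = 5.2%. A between-person CV of 30% becomes √[(1 + 0.30²)(1 + 0.052²) − 1] = 30.5%, and 50% becomes 50.3%. This is immaterial.

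**What adjustment can recover.** With an RH SD of 5 points within each group, the squared correlation between group and RH is 5²/(5² + 5²) = 0.50 for a 35 versus 45 split and 15²/(15² + 5²) = 0.90 for 20 versus 50. The variance inflation of the adjusted group difference, 1/(1 − r²), is 2 and 10 respectively. Adjustment works for a modest imbalance and largely fails for a complete one.

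**The case against.** The strongest reply is that nothing in the plan separates the groups. There is one recruitment stream of up to 60 people, and each is classified only at screening, so mixed enrolment is the natural expectation. No recruitment period is given. A reader might infer from the July 2019 version date and the separate targets that one group will be measured in humid summer air and the other in dry winter air. The documents do not support that, so the 16.5% case is a bound and not a forecast.

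A reader might also reach a larger bias by taking evaporation as proportional to 1 − RH, which gives 0.70/0.50 = 1.40 at 30% versus 50%. That treats the eye as no warmer than the room. Under the assumed temperatures the ratio is 45.18/39.91 = 1.13.

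Further points stand. The objective and Hypothesis 1 concern change within one session, where ambient conditions are largely shared. The saved recordings leave later adjustment possible. The study is a pilot and not intended for regulatory use. The Introduction's remark that evaporimeters usable "under a variety of temperatures and humidities would be extremely useful" reports a general need and is not evidence of a defect here.

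These replies limit the size and likelihood of the problem. They do not supply a humidity range, a balancing rule or a planned use of the recordings, and a calendar imbalance cannot be undone once Visit 2 dates have passed.

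**Conclusion.** The point holds as an unprotected source of confounding in Hypothesis 2, not as an expected bias. Under the assumed 34 C eye and 22 C room, a 35% versus 45% imbalance shifts the group difference by about 6% of the mean rate. With a between-person CV of 30%, that raises the chance of a false finding of higher evaporation in dry eye from 2.5% to about 6%. The 16.5% shift needs a complete 20% versus 50% split. The direction depends on which group is seen in drier air.

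If room climate is stable or the dates mix evenly, no systematic bias arises and the extra noise is negligible. The conclusion rests on evaporation scaling with the vapour-pressure gap and on the goggle returning to room air; the percentages rest on the assumed temperatures, humidities and CVs.

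**What to change.** 1. In Section 4.5.18 and Table 4, take the starting relative humidity and temperature from each saved recording and tabulate them by group. Add the missing baseline comparison of dry eye with non-dry eye participants, with one value per participant, stating how the two eyes and the two baseline sets of Section 4.4.3 are combined. Give a supportive version adjusted for starting vapour-pressure deficit, defined as es at one fixed ocular temperature minus starting RH × es at the recorded temperature. Because the fixed term is the same for everyone, its assumed value does not alter a linear adjustment. State that adjustment cannot separate humidity from group if the two are nearly collinear.

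2. In Section 4.2.2, say that the two groups' Visit 2 sessions will be booked over the same weeks where this is feasible within the 14-day limit of Section 4.4.1.

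The data are already collected. The costs are one degree of freedom in a supportive model, wider intervals when humidity and group are correlated, and some scheduling constraint. Screening for the faster-filling group may have to pause, and that is better done before screening than after it, so that eligible people are not pushed past the 14 days.

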## 2 OBJECTIVES

The objective of the study is to compare the rate of tear evaporation, measured with a novel evaporimeter, before and for one hour after an eye drop containing nano-sized oil droplets has been instilled.

The primary outcome variable for this study are the slopes calculated from the change in relative humidity over time.

Other variables of interest include:

- Ocular Surface Disease Index (OSDI) score
- Comfort (subjective rating)
- Dryness (subjective rating)
- Burning/stinging (subjective rating)
- Tear meniscus height (mm)
- Non-invasive Keratograph® break up time (NIK BUT)
- Lipid layer thickness (TearScience LipiView® II)
- Ocular surface area (mm^2)
- Volume inside the goggle (cm^3)

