## 6 POTENTIAL RISKS AND BENEFITS TO HUMAN PARTICIPANTS

This is a minimal risk study because of the use of marketed products, standard optometric assessments, and the use of two investigational non-invasive devices (the prototype evaporimeter and the modified swimming goggles used to measure volume).

It is possible that participants may experience temporary discomfort associated with the study procedures/devices/eye drops including: eye pain, burning and stinging, blurred vision, sandiness or grittiness, itching, irritation, redness light sensitivity, dryness, itching, crusty eyes, and foreign body sensation.

A dye (fluorescein) normally used to eye exams is being used in this study. Although rare, it is possible that participants may have an allergic reaction to the dye. This could cause discomfort to their eye.

Routine clinical procedures including visual acuity, anterior ocular health assessment, and meibography will be used.

One clinical procedure (evaporimetry) will be conducted with an investigational device consisting of a pair of modified swimming goggles containing a temperature and humidity sensor embedded in each lens of the goggle. This procedure poses minimal risk to the participants as the device is does not touch the eye and the portion of the goggle which will come in contact with the skin surrounding the eye will be cleaned with alcohol wipes between each use. Participants may experience temporary discomfort associated with petroleum jelly including; burning, stinging, irritation, blurred vision, and foreign body sensation.

One clinical procedure (measurement of volume inside the goggle) will be conducted with an investigational device consisting of a pair of modified swimming goggles containing small hole

inserted into the top of each lens. This procedure poses minimal risk to the participants as the device does not touch the eye and the portion of the goggle which will come in contact with the skin surrounding the eye will be cleaned with alcohol wipes between each use. Commercially available saline designed for use with the eyes will be inserted into the goggle. Participants may experience temporary discomfort associated with saline including; burning, stinging, irritation, blurred vision, and foreign body sensation.

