**Table 4: Outcome variables and anticipated statistical procedures**

Variable	Analysis	Statistical test
Tear evaporation rate	Change in relative humidity over time	Slope
Tear evaporation rate/Time	Effect of eye drop	RMANOVA Mauchly's test of sphericity Greenhouse-Geisser p values Tukey HSD post hocs Paired t-test
Tear evaporation rate/ OSDI/ Subjective ratings/ Tear meniscus height/ Non-invasive Keratograph® break up time/ Lipid layer thickness/ Area of the ocular surface	Relationship between tear evaporation rate and OSDI/ Subjective comfort, dryness, and burning/stinging/ Other tear film assessments/ Area of the ocular surface	Pearson correlation – r
Tear evaporation rate/Volume inside the goggle	Relationship between tear evaporation rate and volume inside the goggle	Spearman correlation - rho

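### The primary outcome is an open-minus-closed relative-humidity slope that ignores the temperature saved with each reading, so equal vapour release reads lower in warmer goggle air

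*Combined protocol and SAP*

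**What the plan says.** Section 2 sets the outcome: "The primary outcome variable for this study are the slopes calculated from the change in relative humidity over time". Section 4.5.18 repeats it: "The rate of tear evaporation will be calculated from slope derived from the change in relative humidity over time". It then subtracts the closed-eye rate from the open-eye rate and averages three such differences per eye. Row 1 of Table 4 gives the analysis as "Change in relative humidity over time", with slope as the method.

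Temperature is available throughout. Section 6 describes "modified swimming goggles containing a temperature and humidity sensor embedded in each lens of the goggle", and section 4.5.18 states: "Recordings of the temperature and relative humidity during the measurement will be saved as a word document". No section converts RH with it, adjusts for it, or checks it.

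Two steps limit temperature differences. Section 4.4.3 requires at least 15 minutes of adaptation to the room before baseline readings. Between placements, section 4.5.18 says: "The goggle will be removed and ventilated in front of a fan until the relative humidity returns to baseline levels". No room or goggle temperature range is given.

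The outcome serves two hypotheses in section 3: that "instillation of an eye drop will result in lower tear evaporation rates compared to before the eye drop has been inserted", and that "dry eye participants will have higher baseline rates of tear evaporation compared to non-dry eye participants".

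**The concern.** RH is the vapour present divided by the vapour that the air could hold at that temperature. Warmer air can hold more, so the same release from the eye produces a smaller rise in RH. An RH slope therefore mixes the evaporation rate with the temperature of the goggle air.

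The before/after comparison has the most at stake. There is no randomisation, masking or untreated control, both eyes receive the drop, and the order of time points is fixed. If goggle air were warmer after the drop, the RH slope would fall with no change in evaporation, which is the direction hypothesised. If it were cooler, a real fall would be partly hidden. The group comparison and the correlations depend on values from different people, so differences in goggle temperature between people add scatter.

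The study is also meant to validate the device (section 1) and to inform later sample sizes (section 4.2.1). How the device's output is calculated is worth settling in advance.

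**Working it through.** The plan gives no evaporation, temperature or humidity figure to reproduce. Every temperature, RH level and release below is an assumption.

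**Inputs from the plan.** Readings last 20 s, and there are three open and three closed at each time point. Visit 2 has five time points: two baselines, then 10, 30 and 60 minutes after the drop. That is 6 × 5 = 30 placements, 12 before the drop and 18 after.

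**Formulas.** Saturation vapour pressure (Magnus): es(T) = 6.112 × exp[17.62T / (243.12 + T)] hPa. Saturation vapour density: ρ(T) = 216.7 × es(T) / (T + 273.15) g/m³. RH = 100 × vapour density / ρ(T), so at fixed release the RH slope is proportional to 1/ρ(T).

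**1. Scale factor.** At 25 °C, 216.7 × 31.60 / 298.15 = 22.97 g/m³. At 26 °C, 216.7 × 33.53 / 299.15 = 24.29. The ratio is 0.9455, a fall of 5.4%. The same step gives 0.943 (−5.7%) from 20 °C and 0.949 (−5.1%) from 33 °C. From 25 °C:

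| Goggle air warmer by | Change in RH slope |
|---|---|
| 0.5 °C | −2.8% |
| 1 °C | −5.4% |
| 2 °C | −10.6% |
| 3 °C | −15.4% |

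**2. Does the subtraction remove it?** Assume vapour rises of 5 g/m³ (open) and 2 g/m³ (closed) over 20 s.
- At 25 °C: 100 × (5 − 2) / 22.97 / 20 = 0.653 %RH/s.
- At 28 °C: 100 × 3 / 27.14 / 20 = 0.553 %RH/s, or 15% lower.
- In absolute humidity, both give 3 / 20 = 0.15 g/m³/s.

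Subtraction removes skin evaporation and additive drift shared by the two readings. It does not remove a factor that multiplies both.

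**3. Warming that differs between open and closed readings.** From 25 °C and 50% RH with no release, an extra 0.1 °C changes RH by 50 × [ρ(25)/ρ(25.1) − 1] = −0.28 points over 20 s (−0.17 at 30% RH, −0.39 at 70%). If that offset is the same before and after the drop, then (after − 0.28) − (before − 0.28) = after − before, and it cancels within person. Only a change in the offset between time points biases the contrast. A change of 0.1 °C would be worth 2.8% of an assumed 10-point rise.

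**4. Noise between people.** Let goggle temperature be normal around 25 °C, let cv be the coefficient of variation (CV) this adds to the slope, and let f be the biological CV. Variance inflation is 1 + (cv/f)².

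| Temperature SD | Added CV | Inflation, f = 40% | Inflation, f = 20% |
|---|---|---|---|
| 0.5 °C | 2.8% | 1.005 | 1.02 |
| 1 °C | 5.6% | 1.02 | 1.08 |
| 2 °C | 11.3% | 1.08 | 1.32 |

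**5. Cost of converting.** Simulated with temperature-sensor noise of SD 0.1 °C, one reading per second, a 50% RH start and a 10-point rise, the converted rise gains an SD of 0.22 RH-point equivalents per reading. For the mean of three differences this is 0.22 × √(2/3) = 0.18, or 1.8% of a 10-point rise. For comparison, a 1 °C shift changes a 10-point difference to 9.46, an error of 0.54. On these assumptions, and ignoring lag, the two are equal at a shift of about 0.18 / 0.54 = 0.33 °C.

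**The case against.** The strongest reply is that the temperature story is thin. Each set involves 6 × 20 s = 2 minutes of contact. The sets are separated by other tests, with at least 20 minutes between the baselines and readings at 10, 30 and 60 minutes after the drop. The goggle is hand-held and fan-ventilated between placements. A reader might infer from the 30 placements that heat builds up in the goggle and produces a false drop effect. The documents do not support that: carry-over across those gaps is speculative. Slow room drift remains possible. No section limits or checks it, though to bias the mean result it would have to run the same way in most participants.

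Returning the goggle to baseline RH is also a partial temperature constraint, since RH depends on temperature. It is not a full one, because leftover moisture can offset leftover warmth.

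The repeated baseline could reveal drift. If both baselines are kept as levels in the repeated-measures ANOVA, the post hoc tests compare them. The plan does not say that they will be kept, and the comparison covers only the pre-drop interval.

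Finally, conversion is imperfect because sensor noise and lag enter the converted slope. If goggle air warms steadily, an assumed lag of 2, 5 or 10 s leaves roughly 5–6, 20–21 or 41% of the warming artefact. With fast warming that levels off, conversion can over-correct by some 11–21%, depending on the lag and how it is modelled. Lag error shared by open and closed readings cancels on subtraction. This stands as a reason to report both slopes. It is not a reason to leave temperature unused.

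**Conclusion.** The point holds. The primary outcome carries a temperature scale factor of about 5–6% per 1 °C that the open-minus-closed subtraction cannot remove, although the data to remove it are already saved.

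The consequences are limited:
- **Group comparison and correlations:** avoidable noise, small unless goggle temperature varies between people by about 2 °C or more. A reader might infer bias between dry and non-dry groups. That would need goggle temperature to differ by dry-eye status, which nothing in the documents suggests.
- **Before/after comparison:** biased only if goggle temperature, or the open-versus-closed difference in warming, changes between pre-drop and post-drop time points. A reader might infer that any open-versus-closed temperature difference is enough. It is not, because a stable one cancels within person.

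The physics is standard, but every temperature used above is assumed, so the error in this study is unknown and may be negligible. The change is still worth making: it is specific and nearly free, and this uncontrolled, fixed-order design has no other safeguard against temperature drift.

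**What to change.** In sections 2 and 4.5.18 and in Table 4 row 1, replace the definition with text such as:

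> Each RH reading will be converted to absolute humidity (g/m³) using the temperature recorded at the same time by the same lens. The slope over the 20 s will be fitted, the closed-eye slope subtracted from the open-eye slope, and the three differences averaged for each eye. The RH slope will be reported alongside as a sensitivity analysis.

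Add a table of mean goggle temperature, open and closed separately, by group and time point, so that readers can see whether temperature was stable.

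The cost is one spreadsheet formula on data already collected, with no extra procedure or visit. The price in precision is the sensor noise and lag described above. If the two slopes agree, temperature did not matter and the validation is stronger. If they disagree, the temperature table helps show whether a real shift or a sensor problem is the likelier cause.
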